6.1.3 Ancillary Product

No ancillary products are to be provided for this study.

6.2 Product Use

The CORI Robotics has a user manual (Document ID: 500230, REAL INTELLIGENCE™ CORI™ for Knee Arthroplasty). The purpose of this user manual is to serve as the master reference

Clinical Protocol

A Prospective, Multi-center, Study to Evaluate the Safety and Effectiveness of REAL INTELLIGENCE™ CORI™ in unicondylar knee arthroplasty (UKA) and total knee arthroplasty (TKA) procedures

Study Number: CORI.2019.07

Version: 6.0, 15/Jan/2024

Page: 30 of 122

document for properly trained users in the function and operation of CORI Robotics and its accessories.

In addition, the following devices are packaged with an IFU to ensure that the device is used properly and for the intended purposes:

- IFU REAL INTELLIGENCE™ CORI™ Burs (Document ID: 500172)
- IFU REAL INTELLIGENCE™ CORI™ Flat Markers (Document ID: 500198)
- IFU REAL INTELLIGENCE™ CORI™ Tubing Set (Document ID: 500173)
- IFU REAL INTELLIGENCE™ CORI™ Instrumentation Tray (Document ID: 500229)

The list of reference documents can be found in Appendix 22.2 List of Instructions For Use & User Manuals.

It is the Investigator's responsibility to ensure adherence to the IFU. Sites that are familiar with the use of CORI Robotics / Robotic-assisted surgery systems will be selected so no additional training is required.

6.3 Packaging and Labelling

Packaging and labeling are prepared to meet regulatory requirements. Package integrity and labelling should be verified prior to use of the product and confirmed in the eCRF.

6.3.1 Labelling of Investigational Product

All product components of the CORI Robotics System as well as the Smith+Nephew Knee Implant Systems are commercial products in Europe, UK, India and the United States and are being used as approved. Labeling is done as per the standard commercial packaging. No additional labelling will take place.

6.4 Product Accountability Procedures

This study is a post-market study in Europe, UK, India, and the United States. However, the sponsor may provide the study sites with the CORI Robotics System (Console, Optical Tracking Camera, Foot Pedal, Tablet, Display Monitor, Cart, CORI Instrument Trays UKA & TKA) as well as with reusable instrumentation (CORI Robotic Drill, Point Probe, Femur & Tibia Trackers, Checkpoint Pins). Therefore, the following product accountability procedures will be applied for CORI Robotics supplied to study sites.

In instances where CORI Robotics is supplied to site, the investigational site will maintain an inventory of the IP. The Sponsor or its designee will provide a log(s) to facilitate IP inventory control. The log will contain details of receipt, use, returns etc. of IP. All IP accountability logs must be retained in the Investigator Site File (ISF). These records must be available for inspection by the Sponsor, its designees, or by regulatory agencies at any time.

Clinical Protocol

A Prospective, Multi-center, Study to Evaluate the Safety and Effectiveness of REAL INTELLIGENCE™ CORI™ in unicondylar knee arthroplasty (UKA) and total knee arthroplasty (TKA) procedures

Study Number: CORI.2019.07

Version: 6.0, 15/Jan/2024

Page: 31 of 122

The Study Monitor will ensure that the procedures and records are in place for the appropriate reconciliation of all IP. As part of monitoring, the Study Monitor will check that site personnel are following the proper procedures for accountability and completing all necessary documentation.

No product accountability procedures will be applied for the S+N Knee Implant Systems as these are commercially available products. Nevertheless, the S+N Knee Implant System as well as the individual component reference and lot numbers (femoral component, tibial baseplate and insert) will be recorded in the eCRF.

Overall accountability for the use of the product is the responsibility of the Investigator or designated individual.

Following completion of enrolment all supplied CORI Robotics systems will be returned to S+N.

For details on the CORI Robotics System and reusable instrumentation please refer to Section 6.1.1 Investigational Product.

6.5 Surgical Technique

All study related procedures with the CORI Robotics must be performed according to the user manual (Document ID: 500230 CORI Robotics for Knee Arthroplasty) and according to the according to the surgical technique and IFU of the specific Smith+Nephew Implant System.

- IFU Smith+Nephew Knee Systems (Document ID: 81090287)
- IFU ZUK (Document ID: 81093274)
- IFU STRIDE (Document ID: 50030)
- IFU ANTHEM Total Knee System (Document ID: 81105696)

Surgeons selected to participate in this study will be familiar with the CORI Robotics and have written evidence of training and expertise in the study procedure. If deemed necessary, pre-study cases shall be performed until the surgeon feels comfortable with the system in order to prevent any learning curve during the study. The number of pre-study cases depends on the level of the individual experience of the surgeon. Anonymized CORI Robotics Case Reports will be collected for these pre-study cases as proof of experience. If no pre-study cases are completed the case log of the first study case will be collected and analysed as soon as possible following the surgery to ensure the additional data required for the study has been collected.

7.SUBJECT ENROLLMENT AND WITHDRAWAL

7.1Subject Population

A total of 80 subjects will be enrolled in the study in up to 8 sites in Europe, UK, India and the United States.

- 40 subjects will be enrolled for UKA with the use of the CORI Robotics
- 40 subjects will be enrolled for primary TKA with the use of the CORI Robotics

Clinical Protocol

A Prospective, Multi-center, Study to Evaluate the Safety and Effectiveness of REAL INTELLIGENCE™ CORI™ in unicondylar knee arthroplasty (UKA) and total knee arthroplasty (TKA) procedures

Study Number: CORI.2019.07

Version: 6.0, 15/Jan/2024

Page: 32 of 122

For those subjects, the clinician has decided that the best treatment for the subject is a UKA or TKA facilitated with robotic assisted surgery as a routine medical care. This decision will be made irrespectively of study participation.

The subject will then consent to the study specific treatment with the CORI Robotics System. In case of non-participation, the patient can still receive a robotic assisted UKA or TKA with CORI Robotics or an alternative robotic system (e.g. NAVIO™ Surgical System). It is expected that all subjects will be enrolled within 24 months.

Eligibility criteria are specified to ensure that the subject population of the study represents the target population of the IP.

7.1.1 Vulnerable subjects

No vulnerable subjects will be included in the study.

Clinical Protocol

A Prospective, Multi-center, Study to Evaluate the Safety and Effectiveness of REAL INTELLIGENCE™ CORI™ in unicondylar knee arthroplasty (UKA) and total knee arthroplasty (TKA) procedures

Study Number: CORI.2019.07

Version: 6.0, 15/Jan/2024

Page: 33 of 122

7.2 Inclusion Criteria

Subjects will be considered qualified for enrollment if they meet the following criteria:

1. The subject's treating clinician has decided that REAL INTELLIGENCE™ CORI™ and a compatible Smith+Nephew Knee Implant System is the best treatment for the subject's UKA or TKA and the subject has agreed to the treatment.
2. Subject requires a cemented UKA or TKA as a primary indication that meets either criterion A or B.
 - A. Subject requires a cemented UKA as a primary indication due to any of the following conditions:
 1. Non-inflammatory degenerative joint disease, including osteoarthritis
 2. Avascular necrosis
 3. Requires correction of functional deformity
 4. Requires treatment of fractures that were unmanageable using other techniques
 - B. Subject requires a cemented TKA as a primary indication due to any of the following condition:
 1. Degenerative joint disease, including osteoarthritis
 2. Rheumatoid arthritis
 3. Avascular necrosis
 4. Requires correction of functional deformity
 5. Requires treatment of fractures that were unmanageable using other techniques
3. Subject is of legal age to consent and considered skeletally mature (≥ 18 years of age at the time of surgery)
4. Subject agrees to consent to and to follow the study visit schedule (as defined in the study protocol and informed consent form), by signing the Ethical Committee (EC) or Institutional Review Board (IRB) approved informed consent form.
5. Subject plans to be available through one (1) year postoperative follow-up.
6. Routine radiographic assessment is possible.
7. Subject able to follow instructions and deemed capable of completing all study questionnaires.

Clinical Protocol

A Prospective, Multi-center, Study to Evaluate the Safety and Effectiveness of REAL INTELLIGENCE™ CORI™ in unicondylar knee arthroplasty (UKA) and total knee arthroplasty (TKA) procedures

Study Number: CORI.2019.07

Version: 6.0, 15/Jan/2024

Page: 34 of 122

7.3 Exclusion Criteria

Any one (1) of the following criteria will disqualify a potential subject from participation in the study:

1. Subject receives a CORI Robotics UKA or TKA on the index joint as a revision for a previously failed surgery, or need for complex implants, or any other implant than a standard UKA or TKA (e.g. stems, augments, or custom made devices).
2. Subject has been diagnosed with post-traumatic arthritis.
3. Subject receives bilateral UKA or TKA.
4. Subject does not understand the language used in the Informed Consent Form.
5. Subject does not meet the indication or is contraindicated for UKA or TKA according to specific Smith+Nephew knee system's Instructions For Use (IFU).
6. Subject has active infection or sepsis (treated or untreated).
7. Subject is morbidly obese with a body mass index (BMI) greater than 40.
8. Subject is pregnant or breast feeding at the time of surgery.
9. Subject, in the opinion of the Investigator, has advanced osteoarthritis or joint disease at the time of surgery and was better suited for an alternate procedure.
10. Subject has a condition(s) that may interfere with the TKA or UKA survival or outcome (i.e., Paget's or Charcot's disease, vascular insufficiency, muscular atrophy, uncontrolled diabetes, moderate to severe renal insufficiency or neuromuscular disease, or an active, local infection).
11. Subject in the opinion of the Investigator, has an emotional or neurological condition that would pre-empt their ability or willingness to participate in the study including mental illness, mental retardation, drug or alcohol abuse.
12. Subject, in the opinion of the Investigator, has a neuromuscular disorder that prohibited control of the index joint.
13. Subject is a prisoner or meets the definition of a Vulnerable Subject per ISO 14155 Section 3.55¹

7.4 Screening

Investigators should consecutively screen all subjects presenting with degenerative joint disease of the knee, requiring correction of functional deformity, or treatment of fractures that were unmanageable using other techniques to determine whether they meet all inclusion and none of the exclusion criteria

¹ ISO 14155 Section 3.55 States: Vulnerable subject – Individuals who are unable to fully understand all aspects of the investigation that are relevant to the decision to participate, or who could be manipulated or unduly influenced as a result of compromised position, expectation of benefits or fear of retaliatory response.

Clinical Protocol

A Prospective, Multi-center, Study to Evaluate the Safety and Effectiveness of REAL INTELLIGENCE™ CORI™ in unicondylar knee arthroplasty (UKA) and total knee arthroplasty (TKA) procedures

Study Number: CORI.2019.07

Version: 6.0, 15/Jan/2024

Page: 35 of 122

Participating study sites are required to document all screened subjects considered for inclusion in this study. If a subject is excluded from the study, the reasons for exclusion will be documented in the subject's source documents and noted on the Screening and Enrollment Log. All screening activities that occur prior to consent shall be referred to as pre-screening.

Part of the screening process will include documentation of women's childbearing potential. For women of childbearing potential, study sites will determine whether the subject is pregnant using their standard clinical practice.

7.5 Informed Consent

Before conducting any study procedures or examinations, the purpose and nature of the study should be explained to the subject in their native language. Translations of informed consent documents will be available in the participating countries main language(s).

The subject, or their legally authorized representative, will then **read, sign, and personally date** the IRB/IEC-approved informed consent document(s) (see below for difficulties with reading and writing). Additionally, the individual who obtains consent from the subject will sign and date the informed consent document. A copy of the signed informed consent document will be provided to the subject, a copy will be placed in the subject's medical record, with the original filed in the ISF.

The subject will have sufficient time to consider study participation and ensure all questions have been answered this will usually be at least 24 hours unless approved or documented local site Informed Consent procedures allow for this to be shorter. There is no required interval between the time of consent and the first study procedure being carried out.

If the subject is unable to read, the informed consent document and associated study information may be read aloud to the subject in the presence of an impartial witness. If possible, the subject shall sign and personally date the Informed Consent Form (ICF). Where this is not possible, due to difficulties in writing, the subject shall provide verbal consent to participate in the study. The witness shall then personally sign and date the informed consent form, attesting that the information was accurately explained and that the informed consent was freely given.

Due to the nature of completing Patient Reported Outcome during the study the subject must be able to provide consent. A Legally Authorized Representative signature is not allowed in this study.

ICFs will comply with the Health Information Portability Accountability Act (HIPAA) regulations as well as the EU Global Data Protection Regulation (GDPR) and applicable national regulations and laws.

If new information becomes available during the course of the study that can significantly affect a subject's future health and medical care, Smith + Nephew will ensure that information shall be provided to the subject(s) affected in written form and if relevant, all affected subjects shall be asked to confirm their continuing consent in writing.

Clinical Protocol

A Prospective, Multi-center, Study to Evaluate the Safety and Effectiveness of REAL INTELLIGENCE™ CORI™ in unicondylar knee arthroplasty (UKA) and total knee arthroplasty (TKA) procedures

Study Number: CORI.2019.07

Version: 6.0, 15/Jan/2024

Page: 36 of 122

7.6 Enrollment

Subjects for whom the consent process has been completed and have been treated with the study product are considered enrolled.

Subjects that provided informed consent but do not receive the study treatment for any reason will be considered as screen failure.

7.7 Lost to Follow-up

A subject will be considered lost to follow-up if he/she does not appear for the scheduled study visit for two (2) consecutive visits and does not return for a final visit, and study personnel is unable to contact the subject.

Some actively enrolled subjects will not return for follow-up exams on time. Study personnel must make a reasonable effort to contact the subject and document the following contact attempts before declaring a subject to be lost to follow-up: the subject has been contacted according to the site's policies, but no fewer than two documented phone contacts and one certified letter without response. Copies of all attempts to reach the subjects by mail or email and/or the attempts to contact the subject via other means should be documented, and that documentation should be kept with the subject's source documents.

7.8 Withdrawal

7.8.1 Withdrawal from Treatment

Subjects may be withdrawn early from having the study treatment at a date close to surgery or during surgery for the following reasons:

- At the discretion of the Investigator due to:
 - A change in treatment is clinically warranted
 - An adverse event
 - Any other significant reason identified by the Investigator

Subjects withdrawn from having treatment will not be classed as being enrolled (section 7.6).

Subjects withdrawn from having treatment will be replaced and no further follow-up of the withdrawn subjects is required for the study.

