8.3.4 Safety Endpoints

Safety endpoints include the collection of the following events:

- All adverse events (AEs) and complications occurring from the time of subject enrollment until study termination or study completion including intra-operative adverse events and complications.
- Device related re-intervention
- Device Deficiencies
- Knee implant revision rate

All AEs will be categorized in terms of seriousness and relatedness to the study device or to the surgical procedure (Adverse Events, Serious Adverse Events, Adverse Device Effects, Serious Adverse Device effects). All Serious Adverse Device Effects will be further categorized as Anticipated or Unanticipated. The definitions for each of these categories are based on ISO 14155. (Including hardware and instrumentation), complications, and revisions.

Clinical Protocol

A Prospective, Multi-center, Study to Evaluate the Safety and Effectiveness of REAL INTELLIGENCE™ CORI™ in unicondylar knee arthroplasty (UKA) and total knee arthroplasty (TKA) procedures

Study Number: CORI.2019.07

Version: 6.0, 15/Jan/2024

Page: 42 of 122

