9.1.3 Operation Visit & Discharge (Day 0 up to Day 9)

If any Pre-Operative data is collected on the day of surgery, it must be completed prior to the surgery occurring.

1. Check if there is any change in eligibility of the subject since the pre-operative visit. If the subject is no longer eligible, document as screening failure.
2. Query subject regarding any changes in general health and the use of concomitant medications/therapies.
3. Collect data on the surgical plan: Target Leg alignment as entered into the CORI Robotics.
4. Perform surgery and collect intra-operative data on the appropriate eCRF. This includes but is not limited to the following information:

Clinical Protocol

A Prospective, Multi-center, Study to Evaluate the Safety and Effectiveness of REAL INTELLIGENCE™ CORI™ in unicondylar knee arthroplasty (UKA) and total knee arthroplasty (TKA) procedures

Study Number: CORI.2019.07

Version: 6.0, 15/Jan/2024

Page: 45 of 122

- Knee Implant Disposition (recording of tibial baseplate, insert and femoral component name, reference & lot/batch number)
- Surgical data (e.g. duration, blood loss, surgical approach)
- Collect pre- (with the trial implant in place) and post cementation alignment with the use of CORI Robotics.
- Collect the Subject's CORI Robotics Case Report, generated CORI Robotics Software (Robotics System time, cutting time)

5. Complete discharge eCRF.
6. If any adverse device effects or device deficiencies are observed or reported, they must be recorded as instructed in Section 12 - Adverse Events and Device Deficiencies.
7. Instruct the subject on proper postoperative care/procedures, including any contraindicated treatments/medication(s).
8. Instruct the subject returning to the site for the next follow up visit 6 weeks (42 ± 14 days) after the surgery date.

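### Section 7.8.1 does not separate withdrawal before CORI use from withdrawal after it has begun, so a CORI procedure abandoned for an intra-operative event can leave the safety summaries

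*Combined protocol and SAP*

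**What the plan says.** Section 7.8.1 (Withdrawal from Treatment) provides: "Subjects may be withdrawn early from having the study treatment at a date close to surgery or during surgery for the following reasons". The reasons are left to the investigator and include an adverse event and a clinically warranted change of treatment. The section says that these subjects do not count as enrolled, pointing to 7.6, and adds: "Subjects withdrawn from having treatment will be replaced and no further follow-up of the withdrawn subjects is required for the study".

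Section 7.6 (Enrollment) gives both sides of the enrolment test: "Subjects for whom the consent process has been completed and have been treated with the study product are considered enrolled", and "Subjects that provided informed consent but do not receive the study treatment for any reason will be considered as screen failure".

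On safety, 8.3.4 counts adverse events and complications "occurring from the time of subject enrollment until study termination or study completion including intra-operative adverse events and complications". Section 10.2 defines the safety population (SAF) as subjects treated with both CORI and a Smith+Nephew implant, and 10.5 uses the SAF for every safety endpoint. Section 12.5.1 has related events that are ongoing at the end of participation followed until they resolve or become chronic.

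On recording, 9.1.3 says: "If any adverse device effects or device deficiencies are observed or reported, they must be recorded as instructed in Section 12". Section 12.3 requires adverse events of any kind and device deficiencies to go into the CRF, and 22.7 has the principal investigator record every one.

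**The concern.** Withdrawal during surgery covers two different situations. In the first, a reason to withdraw appears in theatre before CORI is used. An example is an exclusion 1 finding in 7.3, the "need for complex implants, or any other implant than a standard UKA or TKA". Treating that subject as a screen failure and replacing them is ordinary practice. In the second, CORI use has begun and the procedure is then completed another way because of an intra-operative event. Section 7.8.1 does not tell the two apart.

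In the second situation the event being measured can itself be the reason why the subject drops out of the count. The case can leave both the numerator and the denominator of the adverse event summaries, and a new subject takes its place. That loss favours the device, in a study whose secondary objective (5.2) includes safety. Device deficiencies are planned as a listing (10.5), so for them the risk is omission from the listing, not a changed rate.

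**Working it through.** **Step 1. Apply the sections to each kind of case.**

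| Case | 7.6 | 7.8.1 | SAF (10.2) |
|---|---|---|---|
| Withdrawn before any CORI use | Screen failure | Not enrolled, replaced, no follow-up required | Out |
| CORI begun, abandoned, sponsor implant placed | Depends on whether partial use is treatment | Open to being applied | Depends on the same question |
| CORI begun, abandoned, no sponsor implant | Depends on whether partial use is treatment | Open to being applied | Out on its wording |
| Completed with CORI and a sponsor implant | Enrolled | Not applicable | In |

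The first and last rows are settled. In the second row, one analyst could exclude the case under 7.8.1 and another could include it under 10.2, and no section decides between them. In the third row the case is outside the SAF however partial use is read. If such subjects are not enrolled, the collection period in 8.3.4 has no starting point for them, although the same item expressly includes intra-operative events.

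**Step 2. Follow-up.** Section 12.5.1 asks for related events to be followed to resolution or chronicity; 7.8.1 requires no further follow-up. Section 12.5 recommends a visit for unresolved events, and section 19 asks for an End of Study CRF for all subjects. None of these says whether it applies to a subject classed as not enrolled.

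**Step 3. The planned denominator.** Section 11 needs 36 evaluable knees per group and allows 10% attrition: 36 / (1 − 0.10) = 40. This reproduces the plan's figure.

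**Step 4. What one case does to a safety table.** The documents give no rate of abandonment, so assume k abandoned cases in a group, each with one event, and no such event among the 40 completed cases. The exact (Clopper-Pearson) 95% limits are the 2.5% quantile of Beta(x, n − x + 1) and the 97.5% quantile of Beta(x + 1, n − x). For x = 0 the upper limit is 1 − 0.025^(1/n).

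- Left out and replaced: 0/40, upper limit 1 − 0.025^(1/40) = 8.8%
- k = 1 counted: 1/(40 + 1) = 2.4% (0.1 to 12.9%)
- k = 2 counted: 2/42 = 4.8% (0.6 to 16.2%)
- k = 3 counted: 3/43 = 7.0% (1.5 to 19.1%)
- Both groups together, two cases in all: 0/80 (0 to 4.5%) against 2/82 = 2.4% (0.3 to 8.5%)

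**Step 5. How often it could arise.** Let q be an assumed chance that a procedure begun with CORI is abandoned for an adverse event. The chance of at least one such case while a group fills 40 completed procedures is 1 − (1 − q)^40. For q = 0.5%, 1%, 2% and 5% this gives 18%, 33%, 55% and 87%. The mean number, 40q/(1 − q), is 0.2, 0.4, 0.8 and 2.1. A spread this wide shows only that the documents cannot fix the size.

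**The case against.** The strongest reply is that the narrow reading of 7.8.1 is the natural one. The section speaks of withdrawal from having the study treatment and ties non-enrolment to 7.6, which makes screen failures only of those who did not receive it. Both the words about surgery and the adverse event reason can then refer to something found or occurring before CORI is used. SAF membership turns on treatment, so a case with some CORI use and a sponsor implant could be kept in whatever 7.8.1 says. The section also says that follow-up is not required; it does not forbid it.

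This stands in part. A reader might infer that 7.8.1 plainly removes every subject exposed to CORI and withdrawn in theatre. The text does not go that far, since the outcome depends on how treated is read. But the reply rests on a reading that no section states, and it gives no help where no sponsor implant was placed.

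A second reply is that capture is handled elsewhere. Sections 9.1.3, 12.3 and 22.7 require recording. Section 12.1.1 defines adverse events for subjects, users and other persons. Section 12.3 requires unanticipated serious adverse device effects to be reported within 10 working days, and 7.4 has exclusion reasons logged. This also stands: it would be wrong to infer that the events go unrecorded or unreported. Recording an event does not, however, place the subject in the SAF or in a denominator.

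**Conclusion.** The concern holds as a gap with a selective consequence. Sections 7.6, 7.8.1 and 10.2 do not settle the status of a procedure begun with CORI and then abandoned, so a case abandoned for an intra-operative event can drop out of the SAF-based summaries and of follow-up. It is clearly outside the SAF only when no sponsor implant was placed.

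The size is unknown and could be nil. The contrast of 0/40 (0 to 8.8%) with 1/41 = 2.4% (0.1 to 12.9%) assumes one such case in a group and no similar event among completed cases. It shows that at this sample size a single case separates no observed event from a reported one.

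A reader might go on to infer that the alignment result is biased. The documents do not support that. Completed CORI procedures are unaffected, nothing is known about how abandoned knees would align, and the 73.4% reference describes implanted knees (292 of 398 TKAs). No effect on the primary endpoint is claimed.

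**What to change.** Reconcile 7.6, 7.8.1, 8.3.4, 10.2 and 12.5.1 as follows.

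1. Limit the rule on non-enrolment, replacement and no follow-up to withdrawals before CORI use. Define the start of use by one recorded event, for example the checkpoint-definition time stamp in the case log (9.2.7). The sponsor should choose the event.
2. Include every consented subject past that point in the SAF, in adverse event collection and in safety follow-up. Report the number of procedures begun but not completed with CORI, with their reasons, adverse events and device deficiencies.
3. State that the full analysis set (FAS) for alignment remains procedures completed with CORI and a sponsor implant. The FAS is a subset of the SAF, so without this a wider SAF would bring in abandoned cases that have any qualifying post-operative assessment. Abandoned cases may still be replaced for the evaluable count.

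The cost is protocol and SAP wording, safety follow-up of probably a few subjects, and possibly slightly less favourable safety figures. The alignment set and the recruitment target do not change. Nothing here concerns when a surgeon may stop using CORI.
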